5.1 Statistical Considerations

Baseline is the value measured on visit 1 before first administration of investigational product in SAV006-003. For variables/assessments not scheduled to be performed at baseline or that are missing at baseline, the baseline value is the value from the IMPALA (MOL-PAP-002) trial measured closest to visit 1.

Numerical data will be presented using number of subjects, mean, standard deviation, median, range (minimum and maximum), as well as number of missing data (if relevant).

All summary tables for categorical variables will display counts, percentages and number of missing data (if relevant) by treatment group.

All tables will include three treatment arms based on the randomized treatment from the IMPALA trial in combination with the current treatment in the presentation of data. The treatment labels will be:

- MOL OD / MOL INT
- MOL INT / MOL INT
- PBO / MOL INT

Furthermore, all tables will include a total column.

End of trial date is set to the date of completion/discontinuation as entered in the eCRF on the end of trial page.

All listings will be made based on all subjects. They will be sorted by treatment and then subject number. A column showing which analysis sets (FAS/Safety) the subject belongs to, will be included.

Due to early closure of the trial patients will perform the measurements as described in visit 7 even though their last visit might not be visit 7.

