5.2 Data Issues due to Covid-19 Pandemic

To get an overview of the impact the COVID-19 pandemic has on the trial the below output will be presented

- Listing with COVID-19 positive subjects including country and time since trial start to COVID-19 start date
- Listing of all adverse events occurring in COVID-19 positive patients including time of the adverse event relative to the COVID-19 start date
- Table with number of missed key secondary endpoints assessments due to pandemic by treatment and visit. The key secondary endpoints are (A-a)DO₂, 6MWD, SGRQ total, DLCO (% predicted), PaO₂ and DSS
- Table with number of alternative endpoint ascertainment (telephone visits, allowed out of window visits and such) if any due to COVID-19 by treatment and visit
- Listing with all protocol deviations due to COVID-19

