6.1 Exposure

Treatment with molgramostim at least once during the trial (yes/no) will be summarized by treatment.

Exposure will be summarized by treatment showing summary statistics (mean, standard deviation, median, p25, p75, minimum and maximum).

Furthermore, an output will be generated showing number of subjects with ≥ 6 months exposure, ≥ 12 months exposure, ≥ 18 months exposure etc.

Exposure will be defined as number of days from visit 1 to last kit date + 21 days or end of trial date whatever comes first.

For the safety update (see section 8.2) exposure will be calculated as number of days from visit 1 to Last kit date + 21 days or Date of last visit before cut-off for safety update whatever comes first.

Relative exposure will be defined as

$$\text{Relative exposure} = \text{Exposure} / \text{number of days in trial}$$

where exposure is defined above. Relative exposure will be summarized by treatment and listed.

Due to premature trial closure a table with last visit attended will be presented showing number of patients and percentages. For patients where the last visit was entered as visit 7, the original visit they came in for will be presented in this table based on full analysis set. A listing of visits attended will be presented.

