7.2.1 Blood Gas Analysis

The following variables will be assessed from an arterial blood gas sample collected at the timepoints shown in Table 1.

- PaO₂ (mmHg) – arterial partial pressure of oxygen
- PaCO₂ (mmHg) – arterial partial pressure of carbon dioxide
- F_iO₂ – fraction of inspired oxygen

P_{atm} (ambient atmospheric pressure) must be collected using a bedside barometer. The P_{H₂O} (saturated vapor pressure of water at body temperature) will be set to 47 mmHg / 6.266 kPa.

The Aa Gradient (A-a)DO₂ will be calculated centrally using the following formula:

$$Aa\ Gradient = \left(F_i O_2 (P_{atm} - P_{H_2O}) - \frac{P_a CO_2}{0.8} \right) - P_a O_2$$

The Aa Gradient will be summarized by visit. A corresponding mean and with confidence interval (CI) plot over time will be provided. Subjects on supplementary oxygen during blood gas sample are excluded from the relevant visits in the summary.

A corresponding listing by subject and visit will be provided including all subjects regardless of use of supplemental oxygen.

Any Aa Gradients reported in kPa will be converted to a result in mmHg, this will be done using a factor $k=7.5$ ($kPa \times 7.5 = mmHg$).

7.2.2 6-minute Walk Test (6MWT)

Exercise capacity will be assessed using the 6MWT to measure the 6-minute walk distance (6MWD) at the timepoints shown in Table 1.

The 6MWT should be performed twice at each visit in accordance with the European Respiratory Society (ERS)/American Thoracic Society (ATS) guidance.

Data from both tests should be entered in the eCRF. Parameters to be recorded comprise pre and post walk dyspnea score using the Borg (CR-10) Dyspnea Score (including the difference post minus pre dyspnoea score), SpO₂ (%) at start, worst SpO₂ (%) during the walk, distance walked (m), duration of the walk (minutes and seconds), oxygen flow rate if applicable, reason for stopping early (if applicable). For each subject and each visit the results from the test with the longest distance walked will be used in the reporting of the trial.

Distance in meter, Borg score endpoints, and SpO₂ and the desaturation (first SpO₂-worst SpO₂) will be summarized by treatment and visit. Furthermore, number of subjects (N, %) who completed the test will be presented by treatment and visit.

A corresponding mean and CI plot over time as well as a corresponding listing by subject and visit will be provided for each of the endpoints.

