7.2.3 St Georges Respiratory Questionnaire (SGRQ)

The total SGRQ score and component scores (symptoms, activity and impact scores) will be calculated according to the SGRQ scoring manual. Total score as well as the component scores will be summarized by treatment and visit. Corresponding mean and CI plots over time will be provided as well as a listing by subject and visit. The listing will contain both response to the individual questions in SGRQ as well as the total and component scores.

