7.2.4 Whole Lung Lavage

The number of subjects experiencing whole lung lavage (WLL), and the number of WLLs events will be summarized by visit and overall. The summary will also include event rates (95% CI) adjusted for time in trial since visit 1. A separate summary will present the number of subjects and the number of events between IMPALA and IMPALA-X. A WLL event is defined as a WLL procedure performed on a unilateral lung. These events are entered at visit 1 as part of the overall clinical assessment.

Time in trial is defined as the number of days from visit 1 to end of trial date.

Event rates shown as the number of events per subject year and the 95% confidence intervals (CI) of the event rates are estimated using a negative binomial model.

The 95% CI will be estimated using the below piece of code in SAS. Here the dataset *wll_rate* has the number of whole lung lavage by subject in parameter *aval*, and the logarithm of the time of exposure in parameter called *log_dur*. The parameter one has the value 1 (one) for all subjects. The dataset final include the estimated rate (*esti*), and the lower limit of the confidence interval (*lowci*) and the upper limit of the confidence interval (*uppci*).

```
ods output ParameterEstimates=ParameterEstimates;

proc genmod data= wll_rate;

class one;

model aval= one /cl noint dist=negbin offset=log_dur link=log ;

lsmeans one / exp cl;

run;

data exp;

set ParameterEstimates;

where parameter="one";

esti = exp(estimate); * estimate;

lowci = exp(LowerWaldCL); * lower limit of confidence interval;

uppci = exp(UpperWaldCL); * upper limit confidence interval;

run;
```

Furthermore, the whole lung lavage will be summarized by location (left, right or both) and the volume of saline used will be summarized.

A listing of subjects requiring WLL including reasons for WLL, date of criteria met, and date of procedure will be provided.

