- Listing 16.2.6.8 Individual overall clinical assessments (all subjects)
- Listing 16.2.6.9 Individual GM-CSF measurements above lower level of quantification (all subjects)
- Listing 16.2.7.1 Adverse events (all subjects)
- Listing 16.2.7.2 Serious adverse events (all subjects)

Listing 16.2.7.3 Adverse drug reactions (all subjects)

Listing 16.2.7.4 Adverse events leading to treatment discontinuation (all subjects)

Listing 16.2.8.1 Individual haematology (all subjects)

Listing 16.2.8.2 Individual clinical chemistry (all subjects)

Listing 16.2.9.1 Individual vital signs (all subjects)

Listing 16.2.9.2 Individual electrocardiogram (all subjects)

Listing 16.2.10.1 Individual CT scans (all subjects)

13 List of Tables

Section 14.1

Table 14.1.1 Subject disposition (full analysis set)

Table 14.1.2 Number of subjects by visit (full analysis set)

Table 14.1.3 Baseline demographics (full analysis set)

Table 14.1.4 Medical history (full analysis set)

Table 14.1.5 Summary of exposure (months) (safety analysis set)

Table 14.1.6 Summary of cumulative exposure (safety analysis set)

Table 14.1.7 Summary of relative exposure (safety analysis set)

Table 14.1.8 Summary of last visit attended (full analysis set)

Table 14.1.9 Concomitant medication (safety analysis set)

Table 14.1.10. Summary of missed key secondary endpoints assessments due to COVID-19 pandemic (safety analysis set)

Table 14.1.11 Summary of alternative endpoint ascertainment due to COVID-19 pandemic (safety analysis set)

Section 14.2

(14.2.1: Blood gas analysis endpoints)

Table 14.2.1.1 Summary of (A-a)DO₂ (mmHg) (full analysis set)

Table 14.2.1.2 Summary of change from baseline in (A-a)DO₂ (mmHg) (full analysis set)

(14.2.2: 6 minutes walking test endpoints)

Table 14.2.2.1 Summary of 6 minutes walking distance (m) (full analysis set)

Table 14.2.2.2 Summary of change from baseline in 6 minutes walking distance (m) (full analysis set)

Table 14.2.2.3 Summary of pre-walk dyspnoea score (Borg CR10) (full analysis set)

Table 14.2.2.4 Summary of change from baseline in 6 minutes walking distance (m) (full analysis set)

Table 14.2.2.5 Summary of post-walk dyspnoea score (Borg CR10) (full analysis set)

Table 14.2.2.6 Summary of change from baseline in dyspnoea score (Borg CR10) (full analysis set)

Table 14.2.2.7 Summary of SpO₂ at start of walk (%) (full analysis set)

Table 14.2.2.8 Summary of change from baseline in SpO₂ at start of walk (%) (full analysis set)

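### Closing visits entered as Visit 7 are mapped back to their original visit for one table only; the other by-visit outputs have no analysis-visit rule

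*SAP*

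**What the plan says.** SAP 5.1 deals with early closure in one sentence: "patients will perform the measurements as described in visit 7 even though their last visit might not be visit 7". This settles which assessments are done at the closing visit. It does not say which visit the results belong to in the analysis.

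SAP 6.1 shows that some closing visits carry the label Visit 7 in the database and gives the only correction in the plan: "For patients where the last visit was entered as visit 7, the original visit they came in for will be presented in this table". The table meant is last visit attended, listed in SAP section 13 as Table 14.1.8. SAP 6.1 also promises a listing of visits attended, without saying which label it shows.

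The SAP flow chart (Table 1) sets Visit 7 at Month 36, Week 156, with a window of 4 weeks either side. SAP section 2 says the analysis is based on the eCRF database.

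The result sections name only the layout. For oxygenation, "The Aa Gradient will be summarized by visit" (SAP 7.2.1). For quality of life, "Total score as well as the component scores will be summarized by treatment and visit" (SAP 7.2.3). For lavage, "the number of WLLs events will be summarized by visit and overall" (SAP 7.2.4). Protocol section 11 likewise presents data by visit and leaves further detail to the SAP.

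**The concern.** The sponsor recognised that the entered visit and the true visit can differ, and wrote a correction that is expressly limited to one table. For everything else, a programmer working from the eCRF visit and the phrase by visit would put a closing assessment from, say, Month 18 into the Month-36 column.

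Two errors would follow. The Month-36 column, and the last point of the mean plots, would mix shorter follow-up under a three-year label. The earlier columns would lose the subjects whose closing visit fell there. The secondary objectives concern effects of long-term use, so the visit label is how a reader learns what duration a summary describes. SAP 3.2 says the results will form part of a potential future marketing application, although the intermittent regimen will probably not be included in the posology.

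**Working it through.** The plan states no figure to reproduce. The check sets the passages side by side and adds simple date arithmetic.

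**1. Which outputs have a rule**

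| Output | SAP section | Presentation | Rule for a closing visit entered as Visit 7 |
|---|---|---|---|
| Last visit attended (14.1.8) | 6.1 | by last visit | original visit restored |
| Subjects by visit (14.1.2) | 13, title only | by visit | none |
| Missed assessments and alternative ascertainment due to COVID-19 (14.1.10, 14.1.11) | 5.2 | by visit | none |
| (A-a)DO2 | 7.2.1 | by visit | none |
| 6MWT | 7.2.2 | by visit | none |
| SGRQ | 7.2.3 | by visit | none |
| Lavage counts | 7.2.4 | by visit and overall | none for the by-visit part |
| Lung function | 7.2.5 | by visit | none |
| DSS | 7.2.6 | over time | none |
| Overall clinical assessment | 7.2.8 | by visit | none |
| Vital signs, ECG | 8.1.4, 8.1.5 | by visit | none |
| Laboratory data | 8.1.6 | by time point | none |

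The change-from-baseline tables for (A-a)DO2, 6MWT, SGRQ and lung function appear only as titles in SAP section 13, with no visit wording of their own. If they follow the layout of their parent tables, they have the same gap. I found no windowing rule on study day and no separate end-of-trial time point in either document.

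**2. Outputs that do not depend on the label**

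- Adverse events are selected by onset date relative to first and last drug dates (SAP 8.1.2).
- Exposure runs from Visit 1 to last kit date + 21 days or end of trial (SAP 6.1).
- The overall lavage rate uses days from Visit 1 to end of trial (SAP 7.2.4).
- Oxygen supplementation comes from concomitant-medication records, classified against baseline and end of trial (SAP 7.2.7).

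**3. Size of the displacement for one subject**

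From the flow chart, displacement = 156 − scheduled week of the original visit:

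- Visit 2: 156 − 26 = 130 weeks
- Visit 3: 156 − 52 = 104 weeks
- Visit 4: 156 − 78 = 78 weeks
- Visit 5: 156 − 104 = 52 weeks
- Visit 6: 156 − 130 = 26 weeks

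Each subject has at most one closing visit and SAP 3.2 gives 60 enrolled, so at most 60 visits are affected. The actual number is not stated.

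**4. How much true Month-36 data there could be**

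Assumption: final visits took place by 31 December 2020. SAP 3.2 dates only the end of treatment, to the end of 2020. The Visit 7 window opens at 156 − 4 = 152 weeks, or 152 × 7 = 1,064 days. Counting back 1,064 days from 31 December 2020 gives 1 February 2018, the latest Visit 1 date that reaches the window. Protocol 6.1.1 plans the first inclusion for Q1 2018, so true Month-36 data may be sparse.

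Sensitivity: each week by which final visits ran later moves this limit one week later. If they ran to 21 January 2021, the date of SAP version 3.0, the limit moves 21 days, to 22 February 2018, still within Q1 2018.

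**The case against.** The best reply is that the harm is conditional. The SAP nowhere says that the entered label will be used in the other tables. SAP 5.1 acknowledges that the last visit may not be Visit 7, and Table 14.1.8 proves that the original visit can be recovered, so a careful programmer might remap throughout. It is fair that the plan does not prescribe the wrong label. But restricting the correction to one table supports the opposite reading at least as well, and two programmers could produce different Month-36 columns from the same text.

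A second reply is that impact is low: no formal analyses are performed, the primary safety endpoint is untouched, and early closure is visible in the disposition table, Table 14.1.8 and the exposure summaries. All of that stands and limits the severity. Those outputs would warn a careful reader, but they do not correct labels elsewhere. The listing of visits attended is a weaker safeguard than it looks, since the SAP does not say which label it carries.

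Third, a reader might infer that the Month-36 column will hold almost no genuine three-year data. The documents do not establish that. Enrolment dates and final-visit dates are not given, no drug is dispensed at Visit 7, and SAP version 3.0, dated January 2021, still makes final reporting wait for all subjects to have attended a final visit. Final visits in early 2021 are therefore not excluded.

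**Conclusion.** The concern holds as a gap in the analysis specification and should be fixed. The original visit is restored for Table 14.1.8 only; every other output by visit, by time point or over time lacks a rule. Read as written, affected closing assessments would be shown 26 to 130 weeks too late and would drop out of their own column, and Table 14.1.2 could contradict Table 14.1.8.

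The displacement follows from the flow chart alone. The number of subjects affected is unknown and at most 60. That true Month-36 data may be sparse rests on the assumed final-visit date and on the planned, not actual, start of inclusion.

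Two stronger readings should be avoided: that the SAP instructs use of the entered label, and that the safety conclusions are distorted. The first is not in the text. The second fails because the adverse-event and exposure outputs run on dates. By-visit vital signs, ECG and laboratory summaries do share the gap.

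**What to change.** Add a paragraph to SAP 5.1: for all by-visit tables and figures, including Table 14.1.2, the by-visit lavage counts and the COVID-19 by-visit tables, assessments entered as Visit 7 because of early closure are assigned to the original scheduled visit, using the same mapping as Table 14.1.8. A visit that was originally due as Visit 7 stays in the Month-36 column. Listings should show both the entered and the original visit.

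A study-day window or a separate end-of-trial row would also remove the ambiguity, provided one rule is stated for all outputs. The original-visit rule is the cheapest because the mapping is already required. It should also be feasible: flow chart footnote l has subjects leave at the next visit after termination is declared, so the visit they came in for should be known.

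The cost is one paragraph and one derived analysis-visit variable, plus a rerun of any affected outputs already produced. The downside is a sparse Month-36 column, which would reflect the follow-up actually achieved.

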6.2 Concomitant Medication

Concomitant medication is recorded at baseline and during trial. Concomitant medication will be coded using WHODrug version June 2017.

All concomitant medication will be summarized by ATC level 3 and preferred term. All concomitant medication will be listed.

7 Statistical Methodology for Primary and Secondary Endpoints

7.1 Analysis and Presentation of the Primary Endpoint

All adverse events (AEs) occurring after informed consent will be reported in the eCRF. AEs will be coded using the Medical Dictionary for Regulatory Activities (MedDRA) version 21.0.

Events judged by the investigator to be related (including all events that are judged to be possibly related or probably related) to trial treatment are defined as adverse drug reactions (ADRs).

The primary endpoints are

- Adverse events (AEs)
- Serious adverse events (SAEs)
- Non-serious adverse events
- Adverse drug reactions (ADRs)
- Adverse events leading to treatment discontinuation

Adverse events leading to treatment discontinuation are defined as events where action taken with trial drug is marked as *Drug withdrawn in the eCRF*.

All the above adverse events will be summarized by system organ class (SOC) and preferred term (PT), and overall.

The overall summary will include AEs, serious AEs, non-serious AEs, ADRs, AEs leading to treatment discontinuation, fatal AEs and AEs by severity, AEs by action with trial treatment, AEs by outcome.

The summaries by SOC and PT will include number of events, number of subjects, proportion of subjects reporting these events, and rate of events. For each of the primary endpoints, summaries will be given by severity, relationship to trial drug, and outcome.

A summary of treatment emergent adverse events by preferred term with frequency $\geq 5\%$ will be provided together with a summary of treatment emergent non-serious adverse events by preferred term with frequency $\geq 5\%$.

Patient listings corresponding to the summaries, will be provided.

In summaries of adverse events by SOC and PT the tables will be sorted first by SOC and then by PT based on the frequency in the total column.

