5.3. Study Endpoints

5.3.1. Primary Endpoints

Number of AEs, SAEs, adverse drug reactions (ADRs), and AEs leading to treatment discontinuation.

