10.9.2.2. Relationship to Study Drug

An Investigator who is qualified in medicine must make the determination of relationship to the investigational product for each AE. Causality will be assessed as:

Probable

A clinical event, including laboratory test abnormality, with a reasonable time sequence to administration of the IMP, unlikely to be attributed to concurrent disease or other drugs or chemicals, and which follows a clinically reasonable response on withdrawal (dechallenge). Rechallenge information is not required to fulfil this definition.

Possible

A clinical event, including laboratory test abnormality, with a reasonable time sequence to administration of the IMP, but which could also be explained by concurrent disease or other drugs or chemicals. Information on IMP withdrawal may be lacking or unclear.

Unlikely

A clinical event, including laboratory test abnormality, with a temporal relationship to IMP administration which makes a causal relationship improbable, and in which other drugs, chemicals or underlying disease provide plausible explanations.

Not applicable

This assessment can be used e.g. in cases where the subject did not receive any treatment with IMP or if the causality cannot be judged because information is insufficient or contradictory.

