3.3 Subject included

No formal sample size calculation was done as this is an open-label extension trial.

Subjects with aPAP who have completed the IMPALA (MOL-PAP-002) trial will be eligible for this trial. Up to 90 subjects may be included. All subjects in need of treatment will receive inhaled molgramostim.

4 Analysis Sets

All subjects excluding screening failures will be included in the full analysis set.

All subjects with exposure within the trial will be included in the safety analysis set.

The full analysis set will be used for demographics and efficacy summaries and the safety analysis set will be used for safety summaries.

Only recorded data will be analyzed/presented and any subjects who have missing data will only have observed data reported, with no imputation for missing data.

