8.1.1 Analysis and Presentation of Safety Parameters

8.1.2 Adverse Events

All adverse events (AEs) occurring after informed consent will be reported in the eCRF. AEs will be coded using the Medical Dictionary for Regulatory Activities (MedDRA) version 21.0.

Adverse events are considered treatment emergent if the onset of the events is on or after the first exposure date of IMP in this trial and until (estimated) last drug date + 7 days. Last drug date is defined as last kit date + 21 days or end of trial date whatever comes first. Only treatment emergent events will be included in the safety summaries.

Possible or probable related AE's are defined as ADRs.

Adverse events will be presented as described in section 7.1.

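### The ADR primary endpoint leaves out treatment-emergent events coded 'Not applicable' for causality, so it can be understated by an unknown amount, possibly zero

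*SAP*

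**What the plan says.** **Endpoint.** Protocol 5.3.1 names the primary endpoints as "Number of AEs, SAEs, adverse drug reactions (ADRs), and AEs leading to treatment discontinuation".

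**Causality scale.** Protocol 10.9.2.2 has four grades: *Probable*, *Possible*, *Unlikely* and *Not applicable*. The last is described by two examples. It can be used "in cases where the subject did not receive any treatment with IMP", or "if the causality cannot be judged because information is insufficient or contradictory". *Possible* also takes in some poorly documented events, since it allows that "Information on IMP withdrawal may be lacking or unclear". The scale has no grade that simply means unrelated.

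**ADR definition.** SAP 7.1 uses "Events judged by the investigator to be related (including all events that are judged to be possibly related or probably related". SAP 8.1.2 repeats it: "Possible or probable related AE's are defined as ADRs".

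**Which events reach the tables.** SAP section 4 (Analysis Sets) says "All subjects with exposure within the trial will be included in the safety analysis set". SAP 8.1.2 adds "Only treatment emergent events will be included in the safety summaries".

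**Unassessable or missing causality.** The SAP gives no rule. SAP 7.4 and section 8 plan no imputation, and section 9 (Deviations from Protocol) does not mention the matter.

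**The concern.** One code covers two different situations: a subject who had no drug, and an event for which nobody can say whether the drug caused it. The first should be rare in tables restricted to treatment-emergent events in exposed subjects. Of the two uses the protocol names, unassessable causality is then the main one left. The ADR definition omits these events without saying so.

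For a safety endpoint this is the less cautious default. The primary objective is long-term safety, and SAP 3.2 says the results will feed the ongoing safety evaluation and a potential marketing application. Poor information about an event should not lower the reported number of drug reactions without the reader being told how many events are involved.

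**Working it through.** The plan states no expected ADR count, so there is no figure to reproduce. The check follows each grade through the definitions and then bounds the effect.

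**Step 1: trace of the grades (treatment-emergent events, safety analysis set).**

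| Causality grade | In AE/SAE tables | In by-relationship tables | In ADR count |
|---|---|---|---|
| Probable | yes | yes | yes |
| Possible | yes | yes | yes |
| Unlikely | yes | yes | no |
| Not applicable | yes | yes | no |

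The by-relationship tables are 14.3.1.5 (all events), 14.3.1.9 (serious), 14.3.1.14 (non-serious) and 14.3.1.22 (leading to discontinuation). Missing causality has no stated place in the ADR count.

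**Step 2: bound.** Let A be the recorded ADR events and U the treatment-emergent events coded *Not applicable* or missing. Taking the other grades as correct, the count that full information would give lies between A and A + U. If U = 0, or if none of the U events is drug-related, nothing is lost.

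**Step 3: illustration on assumed inputs.** Let r be the recorded ADR share of treatment-emergent events, u the share coded *Not applicable*, and q the share of those that are drug-related. None of the three is in the documents.

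Relative shortfall = u·q / (r + u·q).

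At the upper extreme, q = 1:

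| r | u = 0% | u = 1% | u = 5% | u = 10% |
|---|---|---|---|---|
| 10% | 0 | 1/11 = 9.1% | 5/15 = 33.3% | 10/20 = 50.0% |
| 30% | 0 | 1/31 = 3.2% | 5/35 = 14.3% | 10/40 = 25.0% |
| 50% | 0 | 1/51 = 2.0% | 5/55 = 9.1% | 10/60 = 16.7% |

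With q = 0 every cell is 0. The table shows only how the result depends on the inputs; it does not estimate anything in this trial.

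**Step 4: subject scale.** SAP 3.2 reports 60 enrolled, of whom 55 were on active treatment at termination. The size of the safety set is not stated. One more subject with an ADR moves incidence by 100/60 = 1.67 points, or by 100/55 = 1.82 points.

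**Step 5: can a reader recover the figure from the planned tables?** For events, largely yes: the grades in Table 14.3.1.5 can be added if they are shown separately. For subjects, no. Someone with one *Possible* and one *Not applicable* event appears under both grades, so adding the two subject counts can double count. The combined incidence needs subject-level data. The overview content listed in SAP 7.1 covers severity, action taken and outcome but not relationship, so the number of such events is not a planned overview line.

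**The case against.** **The events are already reported.** SAP 7.1 promises summaries by relationship for each primary endpoint, and the listings show individual events. Nothing in the SAP merges the grades, and Table 14.3.1.18 (ADRs by relationship) is informative only if they are kept apart. This stands, and it means the events are not concealed. It does not supply the combined subject-level incidence or put the number in the overview.

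**The code need not mean unassessable.** The protocol's two uses are examples only, and with no unrelated grade on the scale some investigators may use *Not applicable* for that. Subjects may stop and restart drug (Protocol 6.1 and 7.3.1), yet the treatment-emergent window in SAP 8.1.2 runs from first exposure to the estimated last drug date plus 7 days without a break. An event in a long off-drug gap would qualify as treatment-emergent and could reasonably be coded *Not applicable*. This stands and rules out treating every such event as a drug reaction. Recoding would also replace the investigator's judgement and amount to imputation, which the plan excludes.

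**Such events may be few.** *Possible* already takes some poorly documented events into the ADR count. An opinion on causality is a required AE item (Protocol 10.9.2) and mandatory in the initial SAE report (10.9.3.1), so missing values should be uncommon. This is fair and supports a low priority.

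**No test depends on it.** The trial is descriptive and uncontrolled. That is true, but the ADR count is itself a primary result.

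**Conclusion.** The gap is real and minor. By definition the ADR endpoint excludes treatment-emergent events whose causality could not be judged and was coded *Not applicable*. Against a count that includes them it can only be lower, by an unknown amount that may be zero.

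A reader might infer three stronger things that the documents do not support:

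- **That the SAP classes these events as not drug-related.** It does not. They are left out of the ADR count and remain visible elsewhere.
- **That the count is understated, or by a given percentage.** That would need such events to occur and to be drug-related, and neither number is given. The 0 to 50% span in the illustration comes entirely from assumed inputs (r 10–50%, u 0–10%, q 0–1).
- **That all such events should become ADRs.** The code is too loosely defined for that.

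What holds rests only on the two ADR definitions, the wording of the causality scale and the absence of a handling rule. It is an inexpensive improvement and does not threaten the trial's conclusions.

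**What to change.** Keep the investigator-judged definition (*Possible* or *Probable*) as the main ADR count. State in SAP 7.1 that *Not applicable* and missing causality are outside it, and add to overview Table 14.3.1.1:

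- (a) the number of treatment-emergent events, and of subjects, with causality *Not applicable* or missing;
- (b) a conservative sensitivity ADR row (events, subjects, %) that includes those events, with each subject counted once.

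Do not automatically recode these events as ADRs. Label row (b) as an upper bound, since some of the events may be unrelated or fall in an off-drug gap.

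The cost is one SAP sentence and a small addition to one table, using causality data already collected. The sensitivity figure may be slightly less favourable than the main one. If there are no such events, line (a) shows zero and row (b) equals the main count, which confirms the primary result.
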